Appendix 6-A: Home Treatment example. (PI may suggest other exercise protocols)

Subjects will apply ice or cold pack to the affected area for (times and duration to be confirmed with Clinical Site/PI)

Rehabilitation for Tennis Elbow

<http://www.hughston.com/lha/a.seven.htm>

Rehab For Tennis Elbow: The Super 7

The "super 7" exercises are an important part of treatment for tennis elbow. They are designed to strengthen the muscles in the forearm and increase flexibility through stretching. In most cases these exercises will help relieve elbow pain in about 4 to 6 weeks. Each stretching exercise is held for 15 seconds and repeated 2 or 3 times. This pattern is repeated 5 times a day.

Exercise 1. Stretching the muscles that extend the wrist (extensor muscles): Straighten the arm out fully and push the palm of the hand down so you feel a stretch across the top of the forearm.

Exercise 2. Stretching the muscles that flex the wrist (flexor muscles): straighten the arm out fully (palm side up), and push the palm downward to stretch. Strengthening exercises are performed twice a day following the stretching exercises. To perform these exercises, the patient sits in a chair with the elbow supported on the edge of a table or on the arm of the chair the wrist hanging over the edge. Use a light weight such as a hammer or soup can when performing the strengthening exercises. Repeat the exercises 30 to 50 times, twice a day, but do not push yourself beyond the point of pain.

Exercise 3. Strengthening wrist extensor muscles: Hold the weight in the hand with the palm facing down. Extend the wrist upward so that it is pulled back. Hold this position for 2 seconds and then lower slowly.

Exercise 4. Strengthening wrist flexor muscles: Hold the weight in the hand with the palm up. Pull the wrist up, hold for 2

[figure not shown]
seconds and lower slowly.

Exercise 5. Strengthening the muscles that move the wrist from side to side (deviator muscles): Hold the weight in the hand with the thumb pointing up. Move the wrist up and down, much like hammering a nail. All motion should occur at the wrist.

Exercise 6. Strengthening the muscles that twist the wrist (pronator and supinator muscles): Hold the weight in the hand with the thumb pointing up. Turn the wrist inward as far as possible and then outward as far as possible. Hold for 2 seconds and repeat as much as pain allows, up to 50 repetitions.

Appendix 6-B: Home Treatment Log

	Sets per Day							
	CET Stretch (exercise 1 & 2)					Strenthening (Exercise 3 & 4)	Strenthening (Exercise 5 & 6)	Massage (Exercise 7)
	Set 1	Set 2	Set 3	Set 4	Set 5	Set 1	Set 1	Set 1
1/12/2015								
1/13/2015								
1/14/2015								
1/15/2015								
1/16/2015								
1/17/2015								
1/18/2015								
1/19/2015								
1/20/2015								
1/21/2015								
1/22/2015								
1/23/2015								
1/24/2015								
1/25/2015								
1/26/2015								
1/27/2015								
1/28/2015								
1/29/2015								
1/30/2015								
1/31/2015								
2/1/2015								
2/2/2015								
2/3/2015								
2/4/2015								
2/5/2015								
2/6/2015								
2/7/2015								
2/8/2015								
2/9/2015								
2/10/2015								
2/11/2015								
2/12/2015								
2/13/2015								
2/14/2015								
2/15/2015								
2/16/2015								
2/17/2015								
2/18/2015								
2/19/2015								
2/20/2015								
2/21/2015								
2/22/2015								
2/23/2015								
2/24/2015								
2/25/2015								
2/26/2015								
2/27/2015								
2/28/2015								
3/1/2015								
3/2/2015								
3/3/2015								
3/4/2015								
3/5/2015								
3/6/2015								
3/7/2015								
3/8/2015								
3/9/2015								
3/10/2015								
3/11/2015								
3/12/2015								
3/13/2015								
3/14/2015								
3/15/2015								
3/16/2015								

Appendix 7 – Marketed Materials Information

Appendix 7-A – ITU Systems

[figure not shown]
Clinical Prototype Systems Gen II and Gen III

Power: 3-100 Watts

Frequency: 3 – 10MHz

Energy/Zone: up to 3 Joules (tech. mode)

Appendix 7-B – Diagnostic Ultrasound Imaging System

**SPARK® |**

Point of Care Ultrasound for Superficial Applications
such as Musculoskeletal, Skin, and Breast

*The affordable approach to ultra-high resolution
and deep penetration of the superficial layer.*

CHALLENGE

[figure not shown]
How many times in your practice have you wished that there was a way for you to run a quick scan of something in a patient's superficial layer? How many times have you suspected that a patient had torn cartilage in their knee, a dislocation of a thumb or shoulder, or an early-stage growth on a breast or testicle? Instead of being able to confirm your suspicion on the spot, you were forced to delay diagnosis and treatment while the patient scheduled and underwent comprehensive imaging—often times to confirm what you already knew.

High quality ultrasound for superficial applications have to this point been unaffordable and impractical for Point of Care practices. Requiring large pieces of proprietary equipment and systems, these systems have been cost prohibitive. Until now.

SOLUTION

Spark® is a vital breakthrough in Point of Care imaging for superficial structures. Offering unprecedented sensitivity and ultra-high resolution not found on traditional units 10x or more its price point, Spark is revolutionizing ultrasound for front-line physicians with its performance, price, and value. Highly portable, adaptable, and upgradeable, Spark is powered by a standard PC or laptop and can rapidly integrate with your Patient Information System. Spark is a standardized interface peripheral device that connects to your PC via a standard USB connection; it's as easy to install as connecting a mouse (and almost as simple to use).

Appendix 7-B – Diagnostic Ultrasound Imaging System, continued

WE CALL IT "PLUG AND KNOW"

- 1 Simply attach the Interface to your computer via a Standard USB (Universal Serial Bus) cable
- 2 Automatically install the software Suite from a CD-ROM
- 3 Immediately gain deeper insights into your patients' condition to improve and accelerate your decision making and/or treatment at the Point of Care

Wide interoperability via USB 2.0

Features and Benefits

Excellent Image Quality

- Superb Detail and Contrast Resolution
- Wide Bandwidth Architecture
- ArdentView Image Filters
- Capable of imaging from 5.0MHz - 21MHz (transducer dependent)
- High Frame Rate: up to 139fps

Research

- Human: RF Out Capabilities
- Small Animal:
 - RF Out Capabilities
 - 1KHz M-Mode PRF

Clinical Utility

Superficial Structures

- High Frequency Linear: 5mm - 30mm
- 12MHz Linear Array: 15mm - 45mm

Technical Specifications

Physical Characteristics

- Height: 10.75 in (273 mm)
- Width: 4.75 in (121 mm)
- Length: 19.00 in (483 mm)
- Weight: 22 lbs (10 kg)

Image Storage & Cine

- Dicom Compatible
- Stores Images and Cine as Raw Data
- Export Images as bmp or jpg
- Export Cine as AVI
- Back-up Database to Internal or External Hard Drive, CD, DVD or Network

Power: 100-240 VAC
50-60 Hz input

Transducer Options

- 5.0 - 8.0 MHz Convex Endo
- 9.0 - 14.0 MHz Linear Array
- 14.0 - 21.0 MHz Linear Array

Minimum Computer Requirements

- Windows XP OS: USB 2.0 Port, 256 MB RAM, 1 GB Available Hard Drive Space
- Windows7/ Vista OS: USB 2.0 Port, 500 MB RAM, >1 GHz Duo-Core Processor*, 1 GB Available Hard Drive Space

*assumes Windows7/ Vista Home OS.
More Advanced Versions of Vista may require a faster processor and more RAM

Imaging Modes

- B-Mode
- B-M Mode
- M Mode
- Zoom (Pan)

Measurement Tools

- Distance
- Circumference
- Area
- Volume
- Beats/Minute (m-mode)

CONTACT INFO

To learn more or purchase Spark, please contact Ardent Sound at [contact]
or [contact].

Ardent Sound, Inc.

[name] USA
[contact] [contact] | www.ardentsound.com

Protected by US Patents: 6440071, 6049159, 6120452, 6213948 others pending

[figure not shown]
POLYSONIC® Ultrasound Lotion

The best cosmetic quality lotion for medical ultrasound Polysonic® Ultrasound Lotion

When tough injuries call for gentle treatment, POLYSONIC® Ultrasound Lotion combines the pleasing appeal of a fine cosmetic with superior soundwave transmission. It transmits ultrasonic waves more efficiently than most gels, and is acoustically correct for medical ultrasound procedures.

The rich, moisturizing formulation of POLYSONIC® Ultrasound Lotion is the ideal medium for therapeutic ultrasound when followed with massage. It's kind to your skin as well as to your patients... and won't damage your equipment.

Our multi-purpose lotion, **also available with aloe vera**, is recommended for all medical ultrasound procedures... Another world-class quality product from Parker, a company dedicated to quality.

ISO 13485:2003

Parker Laboratories, Inc.

The sound choice in patient care.™

[contact]

www.parkerlabs.com

© 2012 Parker Laboratories, Inc.

Appendix 7-C – Acoustic Coupling Gel, continued

POLYSOMIC® ULTRASOUND LOTION

Multi-purpose ultrasound lotion with superior coupling efficiency in a pleasing, cosmetic-quality base. Recommended for all ultrasound procedures when a lotion is preferred. Also available, Polysonic Ultrasound Lotion with Aloe Vera.

FEATURES

- Rich, moisturizing formula
- Comfortable and pleasing to patient and ultrasound practitioner
- Acoustically correct for the broad range of frequencies used
- Will not damage equipment or stain clothing
- Hypoallergenic, bacteriostatic
- No formaldehyde

Product #	Package Size
21-08	250 ml (8.5 fl. oz.) dispenser, 12 per box
21-28	3.8 liter (1 US gallon) with dispenser, 4 per case (Dispenser pump not included)
21-50	POLYPAC® contains: 4 Polysonic gallons, 2 dispensers and 1 pump
20-08 with Aloe Vera	250 ml (8.5 fl. oz.) dispenser, 12 per box
20-28 with Aloe Vera	3.8 liter (1 U.S. gallon) with dispenser, 4 per case (Dispenser pump not included)
20-50 with Aloe Vera	POLYPAC® contains: 4 Polysonic with Aloe Vera gallons, 2 refillable dispensers and 1 pump

ISO 13485:2003

Parker Laboratories, Inc.

The sound choice in patient care.™

[contact]

www.parkerlabs.com

TITLE: STUDY TO EVALUATE THE SAFETY, EFFICACY AND TOLERANCE OF INTENSE THERAPEUTIC ULTRASOUND (ITU) FOR THE TREATMENT OF LATERAL EPICONDYLITIS

PROTOCOL NO. and WIRB NO: 20150654

DATE: March 2, 2015

Principal Investigator: [name]

The More Foundation
[name]
[name]
[name]

Sponsor: Guided Therapy Systems
[name]
[name]

Statistical Analysis Plan:

Statistical Methods

Pain Reduction:

Pain level for subjects at the region of interest was self-reported at pre-treatment, used as baseline, and again at each follow-up at 4, 8, 12, and 26 weeks following initial treatment. The pain scale subjects used to identify their level of pain was a 10-point pain scale, where 0 = no pain, 1 = slight pain, through 10 which equates to the patients' worst imaginable pain. The goal for all subjects was to reduce pain by at least 25%. For patients reporting an initial (baseline) score ranging 6-10, this reflects a VAS pain score reduction \geq a 2 point drop; for initial scores ranging 2-5, this reflects a VAS pain score reduction \geq a 1 point drop. Pain scores reported at follow-up timepoints were compared to baseline score for each subject to determine if the goal was met by dividing the difference in the follow-up and baseline pain score by the baseline pain score. The percentage of subjects that met the pain reduction goal was calculated at each timepoint for both groups by dividing the number of subjects that achieved the pain reduction goal at that timepoint by the total number of patients that gave a pain score for that timepoint.

Patient Rated Tennis Elbow Evaluation Score Reduction:

In addition to the 10-point VAS pain scale, patients self-reported answers to questions from the Patient Rated Tennis Elbow Evaluation (PRTEE) questionnaire, which has been standardized for use in research studies to evaluate patient's level of pain and function ^[10]. Scores range from 0-100, with 0 indicating no pain and 100 indicating the worst pain imaginable in a variety of daily activities. Self-reported scores were taken at baseline and each follow-up timepoint. The average score for each timepoint were calculated, and follow-up averages were compared to baseline to calculate the percentage reduction in score.

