Subjects may discontinue from the clinical study at any time. In addition, the Principal Investigator (PI) or designee has the right to withdraw a subject for any reason that is in the best interests of the subject. The subject must inform the Investigator immediately if they intend to withdraw. Subjects may be asked to come to the study facility to complete some end of study procedures.

The Investigator can remove the subject from this study without their consent for any reason, including, but not limited to:

- His/her judgment that any condition or circumstance may jeopardize their welfare or the integrity of the study.
- Their failure to follow the instructions of the investigator(s) (protocol non-compliance)
- Subject BMI exceeds ≥ 35 during the courses of the study.
- If the study is stopped by GTS and/or Principal Investigator of the study prior to completion.

CLINICAL ASSESSMENTS

Assessment of Efficacy

Primary:

The primary endpoint(s) for efficacy and tolerability will be the total score of the PRTEE questionnaire (Appendix 2), subject self-assessment of improvement and satisfaction (SROM-Appendix 3-B), and Visual Analog Scale for Pain (VAS) or Universal Pain Assessment Tool (Appendix 3-C).

Secondary:

The secondary endpoint for efficacy will be a measured reduction in tendon thickness by diagnostic ultrasound, and a physical examination.

PRTEE Questionnaire

The PRTEE questionnaire (**Appendix 2**) evaluates three domains clinically relevant to patients (pain, function, and activity) and was specifically developed to assess the clinical severity of CET tendinopathy. It is composed of 15 questions that cover 3 domains of pain (questions 1 through 5), function for specific activities (questions 6 through 11), and general activities (questions 12 through 15). All questions are scored 0 – 10. Higher scores indicate more severe CET tendinopathy. The PRTEE questionnaire has been validated and shows good test-retest reliability¹⁸

Physical Examination

Medical History: Review patient's medical history questionnaire. Review any diagnostic imaging, tests, or work up listed under longitudinal medical record and centrality. Ask about possible trauma or history of injuries to the symptomatic arm. Review athletic history (tennis, golf, etc) and subject's pre-study exercise regimen (if any). Height, Weight (BMI) will also be documented.

History of Present Illness: Most common complaint is of elbow pain.

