Function will be assessed using three validated response forms: PRTEE - An index of the severity of CET Tendinopathy¹⁸ (Appendix 2), Self-Reported Outcome Measures (SROM)¹⁶.

Level of Activity will be assessed using the activity subscale of PRTEE¹⁸ (Appendix 2). This subscale scores quantitatively the level of difficulty subjects face when they perform basic activities of daily living. It has shown to be an accurate and reliable predictor of the activity level while performing day-to-day activities.

Statistical analysis

Data will be assessed for variance homogeneity and normality. PRTEE¹⁸, and Visual Analog Scale for Pain (VAS) or Universal Pain Assessment Tool (Appendix 3-B) scores will be assessed before and after intervention. The VAS will be used for 2 different assessments: 1. Pain related to physical activity of the symptomatic arm before and after treatment. 2. Pain tolerance of the therapy treatment. Each of these assessments will be documented and evaluated separately.

Aim 2: CET Tendon thickness

Diagnostic ultrasound imaging will be performed with an FDA approved ultrasound scanner (Spark[®] System, Ardent Sound, Inc. – Mesa, AZ, see Appendix 7-B using a coupling gel (Polysonic[®], or AquaSonic[®], Parker Laboratories, Inc., Fairfield, NJ, see Appendix 7-C) by a trained sonographer or physician. Subjects will be treated seated with their arm resting on a structure that is comfortable for the subject and technologist.

CET Tendon thickness is measured before treatment(s) and at each documented assessment (Appendix 1). Paired t tests are used to compare the CET Tendon thickness means between pre- and post-treatment between the symptomatic and treated arm and the asymptomatic and untreated arm. P<0.05 is considered to be statistically significant. Any peri-CET pathology will also be documented.

Aim 3: Assessment of safety and tolerability

Subject self-assessments of treatment tolerability will be conducted immediately after treatments, and at each follow-up visit and phone survey using a 10-point visual analog scale VAS, (Appendix 3-B). The subject will be asked to report their current level of pain and the maximum level of pain experienced since the last treatment. The surveyor will remind the subject of the VAS criteria and record their reply. The VAS is the standard for assessing pain for both clinical and research purposes²².

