Additionally SAEs must be reported immediately to the IRB Title with 24 hours of the site staff becoming aware of the event. The contact details for reporting any expedited AE are given in the Contacts section of this protocol.

In the event that the percent of study related AEs is $\geq 25\%$ for a specific AE symptom, the IRB Title should be notified within 24 hours.

FOLLOW-UP OF ADVERSE EVENTS

If an AE is ongoing at the end of the study, follow-up will be performed until the AE has resolved. Follow-up may take the form of subject visits, a referral to another specialist, site telephone calls to the subject or letters from the treating physician.

The PI or designee must comply with the specific reporting requirement(s) of the ethics committee.

PREGNANCY

Females may not participate in this study if they are pregnant, breastfeeding, were pregnant or gave birth within the last three months or are planning a pregnancy during the course of the study.

GUIDED THERAPY SYSTEMS, CONFIDENTIAL

If the subject thinks they have become pregnant during the study it is important that they inform the study doctor immediately. If the subject becomes pregnant or thinks that they may be pregnant, they will be removed from the study.

STATISTICAL CONSIDERATIONS

SAMPLE SIZE CALCULATION

Up to 25 subjects will be enrolled onto the study to ensure a minimum of 25 subjects complete.

STATISTICAL METHODS

A sample size of 25 per protocol subjects will be required to demonstrate statistical significance (two-sided alpha=0.05; 80% power). Descriptive statistics will be calculated for comparison to the values noted in the existing literature.

MONITORING

The PI agrees that the site will permit, if required, study-related monitoring, audits, IRB/IEC review, and regulatory inspection(s), providing direct access to source data/documents.

Sponsor personnel, or their designees, may monitor the study. The monitor has the responsibility to familiarise the PI and the entire centre staff involved in the study with Therapy procedures. The monitor can visit the clinical study centre on a regular basis such as before the first subject has been enrolled, during the course of the study, and at study completion. The monitor must maintain the confidentiality of the study documents. Regular visits may be made to monitor clinical procedures throughout the study duration.

DATA HANDLING AND RECORD KEEPING

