Appendix 1- Calendar of Events

Procedures	Visit 0 Recruitment -14 to 0 Days	Visit 1 Baseline Assessment Week 0	Visit 2 Week 2	Visit 3 Week 4	Visit 4 Week 8	Phone Survey Week 12	Phone Survey Week 24	Responsibility
PI/C, eligiblity paperwork, exam for inclusion criteria	X							PI/Clinical Coordinator (CC)
X-Ray Scheduled	X							PI or Outside
Ultrasound Imaging		X	X	X	X			GTS
ITU Treatment		X		X				GTS
Focused Physical Exam & Clinical Grading for Epicondylitis severity		X	X	X	X			PI or CC
Subject Patient Rated Tennis Elbow Evaluation		X	X	X	X	X	X	Panelist Week 2-8 / PI or CC Weeks 12 and 24
Self-Assessment Questionnaires: Satisfaction & Improvement		X	X	X	X	X	X	Panelist Week 2-8 / PI or CC Weeks 12 and 24
Physical Therapy		X						PI or CC
Home Heat/Cold & Stretching Program Review		X	X	X	X			PI or CC
Telephone Survey						X	X	PI or CC

GUIDED THERAPY SYSTEMS, CONFIDENTIAL

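### VAS pain, one of three primary measures, is summarised in the SAP only as the share of subjects with at least a 25% fall, with no mean change, confidence interval or reference rate, so the percentage cannot be read as an ITU effect

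*SAP*

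**What the plan says.** The protocol (Clinical Assessments, Assessment of Efficacy) names three primary measures: the PRTEE total, the self-reported improvement and satisfaction items, and VAS pain (or the Universal Pain Assessment Tool).

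The SAP (Statistical Methods, Pain Reduction) gives the VAS one analysis. It sets the target, "The goal for all subjects was to reduce pain by at least 25" percent, and then translates it into points:

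- "For patients reporting an initial (baseline) score ranging 6-10, this reflects a VAS pain score reduction" of at least 2 points.
- "for initial scores ranging 2-5, this reflects a VAS pain score reduction" of at least 1 point.

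The result to be reported is a proportion: "The percentage of subjects that met the pain reduction goal was calculated at each timepoint for both groups". The denominator is the subjects with a score at that timepoint. The next SAP paragraph, on the PRTEE, does plan averages and their percentage reduction.

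The protocol does not fill the gap. Its Statistical analysis paragraph says that PRTEE and VAS "scores will be assessed before and after intervention", after checks of normality and variance, and names no statistic. Its Statistical Methods section adds "Descriptive statistics will be calculated for comparison to the values noted in the existing literature", without a value or source.

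**The concern.** A responder percentage means something only against the percentage expected without the treatment. The plan supplies no such figure, and it cannot be taken as zero, for two reasons.

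- Scores are whole numbers, so a 1-point fall from 4 or a 2-point fall from 8 counts as response, and changes of that size can be ordinary visit-to-visit variation.
- Every subject does home exercises. The protocol's exercise sheet (Appendices 4 and 6-A) says these ease elbow pain for most people within roughly 4 to 6 weeks, which falls inside the follow-up period.

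The proportion also hides how far scores moved and how many subjects got worse. With 25 subjects and no interval, a reader could take an imprecise percentage, part of it noise, as evidence of efficacy on a primary measure.

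**Working it through.** **The plan's own figures.** The plan gives no VAS response rate to reproduce. Its sample size (25, two-sided 0.05, 80% power) is tied to no endpoint, effect or SD. For a paired mean it would correspond to a standardised change of (1.96 + 0.842)/√25 = 0.56, which is not stated.

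**Does the point rule equal 25%?** Percentage = points ÷ baseline.

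| Baseline | Points required by SAP | Percent | Points needed for 25% |
|---|---|---|---|
| 2, 3, 4 | 1 | 50, 33, 25 | 1 |
| 5 | 1 | 20 | 2 |
| 6, 7, 8 | 2 | 33, 29, 25 | 2 |
| 9 | 2 | 22 | 3 |
| 10 | 2 | 20 | 3 |

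The rule is looser than 25% at baselines 5, 9 and 10, and says nothing about baselines 0 and 1.

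**Response with no true change.** Assumptions, since the documents give no VAS distribution or SD: true pain T is constant and uniform over the range shown. Baseline B and follow-up F are T plus independent normal error (SD s), rounded and limited to 0–10, with B ≥ 2 kept; 400,000 draws. Response is (B − F)/B ≥ 0.25, or the SAP point rule. Each cell gives one follow-up visit at s = 0.75 / 1.0 / 1.5.

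| True pain | 25% rule | SAP point rule |
|---|---|---|
| 3–7 | 15 / 20 / 29% | 21 / 26 / 33% |
| 4–8 | 9 / 15 / 24% | 15 / 20 / 29% |
| 5–9 | 6 / 11 / 19% | 10 / 16 / 25% |

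**Hand check.** Treat the observed baseline as error-free and the change as normal with SD 1.5, rounded. Then P(response) = Φ((0.5 − points needed)/SD). One point needed gives Φ(−0.333) = 0.369; two points needed gives Φ(−1) = 0.159. Averaging over baselines 4 to 8:

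- 25% rule: (0.369 + 4 × 0.159)/5 = 20%.
- Point rule: (2 × 0.369 + 3 × 0.159)/5 = 24%.

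For SDs of change from 1.0 to 2.5 the ranges are 12% to 30% and 16% to 33%.

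**Background improvement.** If exercise or natural course alone lowered pain by 1 point on average (an illustration; the documents give no size), the same formula with +1 in the numerator gives, at SD 1.5 under the 25% rule, (0.631 + 4 × 0.369)/5 = 42%. Over SDs from 1.0 to 2.5 it is 38% to 45%.

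**Precision at n = 25.**

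- Responder share, exact (Clopper–Pearson) 95% CI: 15/25 = 60% has limits Beta(0.025; 15, 11) = 39% and Beta(0.975; 16, 10) = 79%. For 10/25 = 40% the limits are 21% and 61%, and the lower limit lies within the no-change range above.
- Mean change: half-width = t(0.975, 24) × SD/√25 = 2.064 × SD/5 = 0.41 SD. For assumed SDs of change of 1.5, 2.0 and 2.5 that is 0.62, 0.83 and 1.03 points.

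**The case against.** Four counter-arguments deserve weight.

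- **Pain is also analysed on a continuous scale.** The PRTEE total is primary and listed first, its pain items make up half the score, and the SAP plans averages for it. The protocol's before-and-after and descriptive sentences do not exclude VAS means. This stands: the gap is that no VAS mean is specified. A reader might infer that cutting the VAS at 25% shrinks 25 subjects to about 16 (25 × 2/π). That is a best-case figure for dichotomising a normal change, and it concerns VAS precision only; the SAP states no VAS test.
- **The size depends on assumptions.** This stands too. Moving assumed true pain from 3–7 to 5–9 cuts the lowest rate from 15% to 6%. The documents support a non-zero rate, not a particular one. A reader might infer that most reported responses will be noise; nothing in the documents shows that.
- **A second group may exist.** The SAP reports the rate by group, and the protocol uses the words controlled, allocation and randomised. Yet its Study Outline gives ITU to every subject and describes no sham or untreated subjects. As written, this is a contradiction and not a reference rate.
- **The mean change has no comparator either.** True: it adds information and an interval, but does not isolate the ITU effect.

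Three stronger readings are tempting but unsupported. The chance of meeting the goal at least once over follow-up would be larger, but the SAP reports each timepoint separately. Baseline scores inflated by a flare on the treatment day would raise the rate, but no document indicates such a flare. A change between Visit 0 and Visit 1 might look like an untreated reference, but that window is at most 14 days and precedes the study's exercise programme. It could not represent 4 to 26 weeks of natural course plus exercise.

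**Conclusion.** The point holds as a gap in specification and interpretation. The SAP gives a primary pain measure one bare percentage, with no mean change, interval or reference rate. With no true change, about 6% to 29% of subjects would meet the 25% definition at a single visit, and about 10% to 33% would meet the SAP point rule. Both ranges assume true pain between 3–7 and 5–9 and a visit SD of 0.75 to 1.5. The mismatch at baselines 5, 9 and 10 rests on no assumption. Because all subjects also exercise, the percentage cannot be attributed to ITU, whatever the noise level. The documents do not show that the responder rate is mostly noise, or that VAS means are ruled out. The changes should be made: they use data already collected.

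**What to change.** Amend the SAP as follows.

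1. Make the paired mean VAS change from baseline, with a 95% CI at each visit, the main VAS analysis.
2. Keep the responder rate as supportive, with an exact 95% CI, beside the share who worsen by the same number of points. The worsening share is context, not an exact measure of noise. Because the threshold depends on the observed baseline, the two shares differ even with no true change (26% worsening against 21% improving under the point rule, for true pain 3–7 and SD 0.75).
3. Make the point rule agree with 25%, either by using the ratio alone or by requiring 1 point at baselines 2–4, 2 points at 5–8 and 3 points at 9–10. Say how baselines of 0 and 1 are handled.
4. Reconcile the SAP's mention of two groups with the protocol. If there is no comparator, state that neither summary separates ITU from noise, natural course or exercise.

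The cost is SAP wording and a few lines of analysis, with no new data. The responder rate will look less favourable.

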Appendix 3-B – Subject Self-Assessment Questionnaire, continued:

VAS: Visual Analog Scale for Pain or Universal Pain Assessment Tool.

UNIVERSAL PAIN ASSESSMENT TOOL

This pain assessment tool is intended to help patient care providers assess pain according to individual patient needs. Explain and use 0-10 Scale for patient self-assessment. Use the faces or behavioral observations to interpret expressed pain when patient cannot communicate his/her pain intensity.

GUIDED THERAPY SYSTEMS, CONFIDENTIAL

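### The SAP's point-drop equivalents for its 25% pain-reduction goal are wrong at baseline scores of 5, 9 and 10 and contradict its own ratio calculation

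*SAP*

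**What the plan says.** Under Statistical Methods, Pain Reduction, the SAP makes three consecutive statements about who counts as a responder.

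1. The goal: "The goal for all subjects was to reduce pain by at least 25" per cent.
2. The goal in points. The upper band opens with "For patients reporting an initial (baseline) score ranging 6-10, this reflects a VAS pain score reduction", and the minimum there is 2 points. The lower band covers baselines 2-5, and its minimum is 1 point.
3. The calculation: the SAP uses the words "to determine if the goal was met by dividing the difference in the follow-up and baseline pain score by the baseline pain score" when it sets each follow-up score against baseline.

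The share of subjects meeting the goal is then reported at each timepoint, out of all those who gave a score at that timepoint.

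The SAP says the instrument "was a 10-point pain scale, where 0 = no pain, 1 = slight pain, through 10". Protocol Appendix 3-B likewise tells staff: "Explain and use 0-10 Scale for patient self-assessment". The protocol contains neither a 25% goal nor a point-drop rule, so it does not settle which statement governs.

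**The concern.** The second statement is offered as a translation of the first, but a fixed drop across a band of baselines is a smaller percentage at the top of the band than at the bottom. At the top of both bands the stated drop is less than 25%. The same subject can then be a responder by the point cut-offs and a non-responder by the ratio.

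Pain is one of several primary measures in the protocol (Assessment of Efficacy, Primary), listed as "Visual Analog Scale for Pain (VAS) or Universal Pain Assessment Tool (Appendix 3-C"). The responder percentage is the only summary of this score that the SAP describes. A programmer could reasonably code the bands as a lookup table, and nothing in the SAP says that the ratio takes precedence.

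**Working it through.** **Inputs.** All come from SAP, Pain Reduction: goal of at least 25%; drop of at least 1 point for baselines 2-5; drop of at least 2 points for baselines 6-10. Scores are taken as whole numbers, as the scale anchors imply.

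**Formulas.** Reduction at the SAP's minimum drop = 100 x drop / baseline. Smallest whole-point drop that reaches 25% = 0.25 x baseline, rounded up.

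| Baseline | 25% of baseline | Smallest drop reaching 25% | SAP's drop | Reduction at SAP's drop |
|---|---|---|---|---|
| 2 | 0.50 | 1 | 1 | 50.0% |
| 3 | 0.75 | 1 | 1 | 33.3% |
| 4 | 1.00 | 1 | 1 | 25.0% |
| **5** | 1.25 | **2** | **1** | **20.0%** |
| 6 | 1.50 | 2 | 2 | 33.3% |
| 7 | 1.75 | 2 | 2 | 28.6% |
| 8 | 2.00 | 2 | 2 | 25.0% |
| **9** | 2.25 | **3** | **2** | **22.2%** |
| **10** | 2.50 | **3** | **2** | **20.0%** |

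The SAP's figures are reproduced at six baselines and fail at 5, 9 and 10.

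**Could another rounding rule explain the bands?** Rounding down fails to give the SAP's drop at 2, 3, 6 and 7. Rounding halves up fails at 10 (2.5 becomes 3). Rounding halves to even fails at 2 (0.5 becomes 0). No single rule gives both bands, and only rounding up respects a minimum of 25%.

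**Direction.** For baselines 2-10 and follow-up scores 0-10 there are 9 x 11 = 99 pairs.

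- Point cut-offs accept (2+3+4+5) + (5+6+7+8+9) = 49.
- The 25% ratio accepts (2+3+4) + (4+5+6+7) + (7+8) = 46.

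The three extra pairs are 5 to 4, 9 to 7 and 10 to 8. On whole-number scores the point cut-offs can therefore only raise the rate. The grid shows which pairs differ; it says nothing about how often they occur.

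**Size.** Excess in the responder rate = (subjects in the three pairs) / (subjects scored at that timepoint).

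| Subjects in the three pairs | 25 scored | 20 scored (assumed) |
|---|---|---|
| 0 | 0 | 0 |
| 1 | 4 points | 5 points |
| 2 | 8 points | 10 points |
| 3 | 12 points | 15 points |

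The 25 is the protocol's planned total, treated here as one group.

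**The case against.** The strongest reply is that the plan as written yields the right rate. Only the third statement describes a calculation, and the point drops read as a gloss on the goal. That is the better reading, and under it no result changes. In addition, no test or success threshold depends on the rate. The protocol's statistical analysis under Aim 1 separately says that pain "scores will be assessed before and after intervention", so the responder rate is not the only planned look at this score. The protocol also uses the scale for two purposes, activity pain and treatment tolerance, and never names a 25% responder rate. All of this stands, and it keeps the point minor.

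Two objections limit the numbers.

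- The documents do not say outright that only whole numbers are recorded. With fractional scores the cut-offs are still too lenient at 5, 9 and 10, but they become too strict at 2, 3, 6 and 7. For example, 6 to 4.5 is 1.5/6 = 25% yet misses a 2-point drop. The mismatch would remain, but the rate could move either way.
- The SAP refers to two groups, whereas the sizes above use one pooled group. In smaller groups each misclassified subject would add more than 4 or 5 points.

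Neither objection makes the stated equivalence true. Reading the drops as approximations does not help either, because the goal is a minimum and three of the nine fall below it.

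**Conclusion.** The concern holds. The point equivalents are wrong at baselines 5, 9 and 10, and they contradict both the 25% goal and the ratio in the following sentence. The severity is minor: the error reaches the results only if the cut-offs are programmed in place of the ratio. In that case, on whole-number scores, the responder rate is overstated by 4 percentage points per affected subject with 25 scored, or 5 with 20 scored. The number affected cannot be estimated from the documents and may be zero. The conclusion rests on whole-number scoring for its direction and on a single pooled group for its size. The failure at the three baselines depends on neither.

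**What to change.** Either delete the point equivalents, or correct them to at least 1 point for baselines 1-4, at least 2 points for 5-8 and at least 3 points for 9-10. In both cases add one definition: a responder has (baseline - follow-up)/baseline >= 0.25. The corrected bands agree with this ratio in all 110 whole-number pairs for baselines 1-10 and follow-up 0-10; both accept 47.

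The corrected lower band starts at 1, whereas the SAP's starts at 2 and leaves baselines 0 and 1 in neither band. The ratio is undefined at baseline 0. This is a separate gap in the SAP's own formula, and the same edit should say how such a subject is counted.

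The sponsor should also confirm which rule produced any rate already calculated.

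The cost is one edited sentence and one short definition, with no new data. The rate may be slightly less favourable if the point cut-offs would otherwise have been used.
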